## **Appendix D Diabetic ketoacidosis**

### **Recognizing diabetic ketoacidosis**

Diabetic ketoacidosis, including atypical (euglycemic) DKA, is the most serious emergency in patients with T1D and T2D. Common precipitating factors include infections, intercurrent illnesses, psychological stress and noncompliance with insulin therapy. Clinical features of DKA at presentation can be nonspecific; however most patients complain of polydipsia and polyuria for several days before onset of DKA. Symptoms of DKA include rapid weight loss, nausea or vomiting, stomach pain, excessive thirst, fast and deep breathing, confusion, unusual sleepiness or tiredness, a sweet smell to the breath, a sweet or metallic taste in the mouth, or a different odor to urine or sweat.

It is possible that GI or other AEs occurring with sotagliflozin may mask presenting symptoms of DKA. Because sotagliflozin lowers blood glucose by insulin dependent SGLT1 and SGLT2 inhibition, it is possible for DKA to be present with normal or low blood glucose. Therefore, the Investigator must still consider a DKA event even if blood glucose is low or normal.

More information can be found in the sotagliflozin IB.

If DKA is suspected or confirmed, study treatment should be stopped immediately and should not be re-started unless another cause for the ketoacidosis is identified and resolved.

Caution should be exercised in patients with risk factors for ketoacidosis and inform patients of the risk factors. These include low reserve of insulin-secreting cells, conditions that restrict food intake or can lead to severe dehydration, a sudden reduction in insulin or an increased requirement for insulin due to illness, surgery or alcohol abuse.

In addition, IMP administration should be stopped in patients in hospital for major surgical procedures or due to serious illness.

Whenever AE data is collected or the patient reports DKA or intercurrent illness (including infections), generalized weakness, increased weight loss, GI symptoms including nausea, vomiting, or abdominal pain or other symptoms or signs that the Investigator believes may be consistent with DKA, the site will determine if an assessment for DKA, such as assessing blood BHB, is appropriate. If BHB or other laboratory testing confirms the presence of metabolic acidosis, then the "Possible DKA" e-CRF will be completed.

#### **Patient communication cards will be printed with the following:**

"If you have any of these symptoms on the list, then contact your study site immediately for assistance with managing your diabetes:

- Inability to maintain oral intake
- Generalized weakness

- Abdominal (belly) pain
- Increased weight loss
- Fever
- Frequent urination, including at night
- Fruity-scented breath
- Confusion
- Acute illness
- Consistently elevated blood glucose
- Feeling very thirsty or drinking a lot
- Nausea or vomiting
- Having trouble thinking clearly or feeling tired.

It is possible to have DKA even if your blood glucose is not elevated. Regardless of your blood glucose level, if you have any of these symptoms on the list, then contact your study site regarding the need to be evaluated for possible DKA, which will include specific blood testing. If your study site is closed and your study doctor is not available, go to the nearest emergency room for evaluation.

If you are scheduled for a procedure or surgery that requires you to not take any food or liquids, please contact your study doctor for instructions on continuing study drug. In such cases your study doctor may advise you NOT to take your study drug from the day prior to the procedure or surgery until after the procedure or surgery is complete, and you are taking food and liquids as you normally do.”

Whenever adverse event data are collected or the patient reports DKA or intercurrent illness (including infections), generalized weakness, increased weight loss, GI symptoms including nausea, vomiting, or abdominal pain, or other symptoms or signs that the Investigator believes may be consistent with DKA, then the site will determine if an assessment for DKA, such as assessing blood beta-hydroxybutyrate level (BHB), is appropriate. If BHB or other laboratory testing confirms presence of metabolic acidosis, then the “Possible DKA” e-CRF will be completed.

## **Appendix E Country Specific Changes**

The history of Country specific amendments in Canada) for this amended protocol are irrelevant because the current amendment 3 will be implemented in the US only.

## Appendix F Protocol Amendment History

The summary of changes for the current amendment is located above immediately following after the Clinical Trial Summary.

### 20.1.1 Amended Protocol 1 based on Amendment 1: 09-Jan-2018

#### REASON FOR AMENDMENT:

- **Change to the duration of the Screening Period from 10 days to 21 days**

In Section(s): tabulated clinical trial summary, sections 1.1., 1.2 and 1.3, and section 6.2  
Rationale: Increase flexibility for sites and patients.

- **Change to the duration of the interval from discontinuation of intravenous diuretics to randomization from 4 days to 7 days**

In Section(s): tabulated clinical trial summary, sections 1.1, 1.2 and 1.3, and section 6.2  
Rationale: Increase flexibility for sites and patients.

- **Change to Cohort sample size: Approximately 15 patients in each of Cohorts 1 and 2, and approximately 51 patients in Cohort 3.**

In Section(s): tabulated clinical trial summary, sections 1.2 and 1.3, section 6.2, section 7.1 and section 13.

Rationale: Safety for patients is assessed on an ongoing basis by the DMC, which also has the ultimate decision for up-titration from Cohort 1 to Cohort 2, and from Cohort 2 to Cohort 3. The DMC might determine that the absence of any significant adverse events in a sufficient number of patients on sotagliflozin might be sufficient to allow progression to the next Cohort, or similarly to request expansion in the number of patients exposed to IMP.

- **Change to the inclusion/Exclusion criteria**

In section(s): tabulated clinical trial summary, sections 7.2 & 7.3 of the protocol  
Rationale:

- **I01.** Clarified to indicate that written consent should be obtained during the screening period.

- **I03.** Expanded to include subjects admitted to appropriate inpatient and specialized units where heart failure patients are often safely assessed and screened, and to add increase in weight as one of the qualifying criteria for congestion as this is frequently an indicator of worsening heart failure in chronic heart failure patients. Clarified that treatment with intravenous diuretics is a requirement for consideration of patients to randomization whereas it is not important whether they receive bolus or infusion of drug.

- **I04.** Removed to expand eligibility to patients with new onset heart failure, as treatment with sotagliflozin may also have significant benefits on fluid volume redistribution in eligible congestive and hemodynamically stable patients. New onset

heart failure patients at highest risk will be excluded based on E3-5.

- **E07.** Clarified birth control requirements for male participants.
- **E08.** Simplified for ease of understanding to indicate requirement for intravenous diuretics between screening and randomization, and transition to oral diuretic treatment.
- **E09.** Consolidated criteria for hemodynamic stability at randomization.
- **E03.** Corrected to also account for patients with worsening heart failure that may be admitted to a heart failure unit or infusion center rather than a hospital.
- **E04.** Added and clarified that patients with uncomplicated revascularization following a recent myocardial infarction (index MI, within 1 month) are eligible, as the risk in those patients is significantly less compared to those without revascularization during the index MI or with procedures associated with complications.
- **E05.** Adapted to harmonize with E04 and to indicate that patients who had or scheduled to have a procedure, such as percutaneous coronary intervention or other cardiac intervention, may be eligible if they are stable and congested and in need of diuretic treatment.
- **E12.** Any moderate or severe respiratory disease is an exclusion. Oxygen therapy requirement is redundant in this context.
- **E14.** Corrected previous omission to allow one repeat lab at screening for amylase and/or lipase
- **E15.** Removed, as each case should be individually assessed based on multiple cardiorenal variables. Added instructions in Section 8.8 (Concomitant Medication).
- **E16.** Modified, as only patients with severe or persistent GU infections at randomization may need to be excluded. GU infections associated with SGLT2-inhibitors are described as mainly mild to moderate in intensity and respond to standard treatment. (European Medicines Agency. Jardiance (empagliflozin) public assessment report. March 2014; European Medicines Agency. Forxiga (dapagliflozin) public assessment report. September 2012; European Medicines Agency. Canagliflozin public assessment report. September 2013.)
- **E18.** Removed, text consolidated with E11.

**- New Exclusions added in response to Health Authority/Ethics Committees' feedback:**

- Exclusion of persons dependent on the sponsor, investigator or study site is added.
- Exclusion for diabetic patients at high risk of lower limb amputations
- **Change to the classification of Iodinated-Albumin and Deuterium Oxide from “Noninvestigational medicinal product” to “Non-medicinal product”**

In section(s): Tabulated summary and 8.2

Rationale: Correction, as recommended by Health Authority reviews in European Union countries

In addition, other minor changes are listed in the description of changes

## 20.1.2 Amended Protocol 2 based on Amendment 2: 14-Mar-2018

### REASON FOR AMENDMENT:

- **Correction of nomenclature for the non-investigational medicinal products**

In section(s): tabulated clinical trial summary, sections 9.6, 9.7, 9.11, 11.2.3, 11.3.1, of the protocol

Rationale:

Correction (and reversal to the original classification) from 'Non-medicinal product' to 'Noninvestigational medicinal product', to be consistent with generally accepted nomenclature, following clarification of the classification for deuterium oxide and radiolabeled albumin.

- **Change to the inclusion/Exclusion criteria**

In section(s): tabulated clinical trial summary, section 8.3 of the protocol

Rationale:

E02. Added exclusion of persons sectioned due to an official or court order (as per section 1.61 of the ICH/GCP Guideline E6.)

- **Added clarification for patients who may be stable and improving but need to continue their treatment in hospital or transferred to a unit, center or ward, such as rehabilitation ward, during the study**

In section(s): Sections 1.2, 1.3, 13.1 of the protocol

Rationale:

Added guidance on how sites could handle the Visit schedules for those patients who may need to continue part or all of their treatment within a hospital or related setting

- **Added option for exploratory analysis to be performed for safety reasons**

In section(s): 6.3 Interim analysis, 14.1 Determination of sample size, 14.10 Interim analysis

Rationale:

*Ad hoc* exploratory analysis may be performed for safety reasons and/or if requested by an institutional review board or ethics committee

- **Removed option for a legally-acceptable representative to sign the consent form**

In section(s): 15.2 Informed Consent

Rationale:

Only patients themselves can provide consent to participate in this study

In addition, other minor changes are listed in the description of changes

Signature Page for VV-CLIN-0463139 v7.0  
pdy15079-16-1-1-amended-protocol03

Approve & eSign	 Clinical 02-Aug-2019 01:16:41 GMT+0000
-----------------	---

1 OVERVIEW AND INVESTIGATIONAL PLAN

This statistical analysis plan (SAP) provides a comprehensive and detailed description of strategy and statistical techniques to be used to analyze data for SAR439954 study protocol PDY15079 approved on 05 Jul 2017 amended on 14 Mar 2018. The purpose of the SAP is to ensure the credibility of the study findings by prespecifying the statistical approaches to the analysis of study data prior to database lock.

1.1 STUDY DESIGN AND RANDOMIZATION

This is a phase 2, multi-center, multinational, randomized, double-blind, placebo-controlled, parallel arm trial of the safety, tolerability and pharmacodynamic activity of sotagliflozin in hemodynamically stable patients with worsening heart failure. An initial cohort of patients (Cohort 1) will receive sotagliflozin 200mg (n=approximately 10) or placebo (n= approximately 5) for fourteen days. Following safety monitoring and review by the data monitoring committee (DMC), Cohort 2 will receive sotagliflozin 400mg (n= approximately 10) or placebo (n= approximately 5) orally for fourteen days. Following completion of Cohort 2 and review of safety and tolerability by the DMC, patients in Cohort 3 will be allocated to sotagliflozin 200 mg, (n= approximately 17) 400 mg (n= approximately 17) or placebo (n= approximately 17) orally for fourteen days. This is summarized in [Table 1](#).

Table 1 - Cohort randomization and allocation scheme

Cohort	Randomization	Sotagliflozin 200 mg	Sotagliflozin 400 mg	Placebo	Total N
1	2:1	10	0	5	15
2	2:1	0	10	5	15
3	1:1:1	17	17	17	51
Total N		27	27	27	81

Patients are randomized to receive either sotagliflozin or placebo, according to the randomization scheme for each Cohort as described below:

- Cohort 1: Sotagliflozin 200 mg : Placebo = 2:1
- Cohort 2: Sotagliflozin 400 mg : Placebo = 2:1
- Cohort 3: Sotagliflozin 200 mg : Sotagliflozin 400 mg : Placebo = 1:1:1

For each randomized patient, the IRT will allocate a treatment package number corresponding to the treatment group assigned.

1.2 OBJECTIVES

1.2.1 Primary objectives

The primary objective of this study is to assess the safety and tolerability of sotagliflozin, added to the standard of care treatment, in hemodynamically stable patients with worsening of heart failure, compared to placebo.

A co-primary objective of this trial is the estimation of the effect of sotagliflozin, when added to the standard of care treatment, on changes in plasma volume, as assessed by direct (indicator dilution) and indirect (hemoconcentration) methods, in hemodynamically stable patients with worsening of heart failure, compared to placebo.

1.2.2 Secondary objectives

The main secondary objectives of this study are:

- To explore the effect of sotagliflozin, added to standard of care treatment, on erythropoiesis, as assessed by changes in plasma erythropoietin levels, in hemodynamically stable patients with worsening of heart failure, compared to placebo.
- To explore the effect of sotagliflozin, added to standard of care treatment, on changes in plasma NT-proBNP levels, in hemodynamically stable patients with worsening of heart failure, compared to placebo.

1.2.3 Exploratory objective

The exploratory objectives of this study are to explore the effect of sotagliflozin compared to placebo treatment, in hemodynamically stable patients with worsening of heart failure, on the following endpoints:

- Change in total body water from baseline to 14 days
- Change in uric acid from baseline to 14 days
- Change in beta-hydroxybutyrate from baseline to 14 days
- Change in total blood volume from baseline to 14 days
- Change in red cell mass from baseline to 14 days
- Percentage of patients within 15% of ideal blood volume on study day 14
- Blood pressure, sitting (SBP and DBP), at day 14 compared to baseline

1.3 DETERMINATION OF SAMPLE SIZE

The sample size determination and the statistical power are estimated based on the main PD endpoint of plasma volume. The following assumptions are used for the estimation of the sample size, based on published data of the plasma volume (PV) response following 12 weeks of treatment with SGLT2 inhibition, relative to the placebo response, in non-HF patients:

- 10% reduction in plasma volume from baseline, with an averaged value of 0.47 liters difference for the sotagliflozin group to the end of 2-week treatment between the sotagliflozin and placebo groups, respectively;
- The placebo response might be highly variable in this population. In the study by Lambers Heerspink et al, PV increased by approximately 2% at the end of the 12 week treatment period in the non-HF population. For the purpose of sample size estimation in this study, the assumption is that PV will be reduced by 1% in the placebo group.
- A common standard deviation (SD) of 0.8 liters for the reductions from baseline to the end of 2-week treatment in plasma volume for both groups;
- A t-test at 1-sided $\alpha=0.05$; or equivalently, 2-sided $\alpha=0.10$;

Based on the above assumptions, it is estimated that, with a total of 81 patients with complete evaluations, or 27 patients per arm, the study will have a 71% power to detect an approximately 9 percentage point difference (10% vs 1%) in the reduction from baseline in plasma volume at the end of 2-week treatment for the main comparison of the pooled sotagliflozin (200 mg and 400 mg) group versus placebo. With 60 evaluable patients, or 20 patients per group, the study power is 60%. The calculated sample size refers to the size of completers who have plasma volume values at both baseline and end of the 2-week treatment.

[figure not shown]
Furthermore, interim analyses will be performed following Cohort 2 and during Cohort 3 for the purpose of exploratory analyses of pharmacodynamic, pharmacokinetic or safety variables, and sample size re-estimation, partly based on the observed variability of changes in plasma volume and/or hemoconcentration. Exploratory analyses may also be performed earlier for safety reasons, or if requested by the DMC or institutional ethics committees. In that case, the analysis will not result to any changes to the protocol.

The study population will consist of at least 30% diabetic patients.

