## 8 SELECTION OF PATIENTS

### 8.1 NUMBER OF PATIENTS PLANNED

The study population will consist of male and female patients, 18 years and older, admitted to the hospital or heart failure unit or infusion center with worsening of heart failure requiring administration of intravenous diuretics, as per inclusion and exclusion criteria detailed below.

A subject who received treatment and prematurely ends his/her treatment will be replaced in order to have approximately 64 evaluable observations.

A patient should not be randomized more than once.

Re-screening is allowed once during the current hospitalization, if in the opinion of the investigator, the change in the clinical status of the patient allows inclusion in the trial. Patients that failed screening during the first encounter for this trial can be rescreened during subsequent hospitalizations or visits to the infusion or heart failure units.

A patient that requires re-hospitalization will be discontinued from IMP administration. Every effort will be made to follow up the progress of the patient and continue collection of relevant safety data, as appropriate and when applicable, and as judged by the Investigator with potential input from the DMC and Sponsor, as appropriate for each case, for the same follow up period (approximately 2 weeks) as for all other patients participating in the trial. In those cases, the follow up procedures and/or visit to clinical site should be followed as per study flow chart in [Section 1.2](#). Only if judged appropriate by the Investigator and Sponsor, and in the absence of safety signals, the patient will be allowed to participate in some or all of the EOT study procedures.

For all patients, GFR will be calculated from the serum creatinine (sCr; mg/dL) and age (years) via the abbreviated Modification of Diet in Renal Disease (MDRD) equation (20):

$$GFR = 186 (sCr)^{-1.154} (age)^{-0.203} (1.212 \text{ if black}) (0.742 \text{ if female})$$

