## **14 STATISTICAL CONSIDERATIONS**

### **14.1 DETERMINATION OF SAMPLE SIZE**

Sample size is based on empirical consideration. No formal sample size calculation has been performed.

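### SAP 1.3 labels 0.47 L as the between-group difference although its powers fit about 0.42 L, and those powers belong to an 81-patient design the protocol has replaced

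*SAP*

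**What the plan says.** SAP 1.3 bases its power on plasma volume. Its first assumption opens with "10% reduction in plasma volume from baseline" and continues, in the same bullet, "with an averaged value of 0.47 liters difference for the sotagliflozin group to the end of 2-week treatment between the sotagliflozin and placebo groups". For placebo, "the assumption is that PV will be reduced by 1% in the placebo group". The variability is "A common standard deviation (SD) of 0.8 liters", and the test is a t-test at one-sided 0.05.

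For 81 completers, 27 per arm, with both sotagliflozin doses pooled against placebo, the SAP says "the study will have a 71% power to detect an approximately 9 percentage point difference (10% vs 1%) in the reduction from baseline". It gives 60% for 60 evaluable patients, 20 per group. Its N counts only patients with plasma volume at both baseline and end of treatment.

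SAP section 1 says the plan is written to the protocol as amended on 14 March 2018. SAP Table 1 has cohort 3 at 1:1:1 and 27/27/27 = 81 patients overall.

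The current protocol (Amended Protocol 03, August 2019) differs. Table 1 and section 9.4 make cohort 3 a 1:1 comparison of 400 mg and placebo, with totals of 10 on 200 mg, 27 on 400 mg and 27 on placebo. Section 8.1 replaces early discontinuations "in order to have approximately 64 evaluable observations". Section 14.1 says "No formal sample size calculation has been performed". Section 12.3 still speaks of 81 patients completing at least 12 days.

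**The concern.** Taken literally, the bullet puts 0.47 L between the two groups, while the power sentence uses a 9-point gap. If 0.47 L is 10% of baseline, 9 points is a smaller number of litres, so both cannot be the treatment difference. A reader who takes the litre figure will neither recover the stated power nor know what effect the trial was planned to detect.

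Separately, the only power statement in either document describes arms that are no longer being recruited. Change in plasma volume is a co-primary objective, and SAP 2.6.2 makes the pooled one-sided 0.05 comparison its primary analysis. A null result set beside the SAP would be judged against 71% (or 80%, using the literal 0.47 L), which the current design does not provide.

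**Working it through.** **Inputs.** SD 0.8 L, t-test, one-sided alpha 0.05, pooled comparison, responses of 10% and 1%, and the 0.47 L figure: all SAP 1.3. Arm sizes: SAP 1.3 (54 vs 27; 40 vs 20) and protocol Table 1 (pooled 10 + 27 = 37 vs 27; 400 mg alone 27 vs 27).

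**Formula.** SE = 0.8 × √(1/n₁ + 1/n₂); noncentrality λ = difference / SE; df = n₁ + n₂ − 2; power = P(noncentral t with df and λ exceeds the one-sided 5% critical value).

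**Step 1: the candidate differences.** If 0.47 L is the 10% fall on sotagliflozin, baseline is 0.47 / 0.10 = 4.7 L (inferred). The 1% placebo fall is 0.047 L. The difference is 0.47 − 0.047 = 0.423 L, or 0.42 L rounded. The literal reading is 0.47 L.

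**Step 2: the SAP's own figures.**

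- 54 vs 27: SE = 0.8 × √(1/54 + 1/27) = 0.1886, df = 79, critical t = 1.664.
- 40 vs 20: SE = 0.8 × √(1/40 + 1/20) = 0.2191, df = 58, critical t = 1.672.

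| Difference | λ, 54 vs 27 | Power (stated 71%) | λ, 40 vs 20 | Power (stated 60%) |
|---|---|---|---|---|
| 0.42 L | 2.227 | 71.3% | 1.917 | 59.9% |
| 0.423 L | 2.243 | 71.9% | 1.931 | 60.4% |
| 0.47 L | 2.493 | 79.6% | 2.145 | 68.3% |

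Solving backwards, 71% needs 0.418 L and 60% needs 0.421 L. Both stated powers therefore come from a difference of about 0.42 L. The literal 0.47 L overshoots each by 8 to 9 points.

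**Step 3: other routes to the stated powers at 0.47 L.**

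- Two-sided 0.05 t-test: 69.2% (54 vs 27) and 56.0% (40 vs 20). The second figure fails.
- Pairwise t-test: 68.6% (27 vs 27) and 57.1% (20 vs 20). Both are more than 2 points low.
- Pairwise normal approximation: 69.6% and 58.4%. This is near, but it is neither the test nor the comparison the SAP names.

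**Step 4: the current design.**

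- 37 vs 27: SE = 0.2025, df = 62.
- 27 vs 27: SE = 0.2177, df = 52.

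| Comparison | 0.42 L | 0.423 L | 0.47 L |
|---|---|---|---|
| Pooled, 37 vs 27 | 65.8% | 66.3% | 74.2% |
| 400 mg alone, 27 vs 27 | 60.2% | 60.7% | 68.6% |

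No cell equals 71%. At the difference the SAP appears to have used, the pooled comparison loses about 5 points.

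**Step 5: tracer availability.** Protocol 10.1.2 limits the labelled-albumin method to sites with the capacity and lets patients decline it, but gives no expected uptake. As an assumption, at 0.423 L pooled: full uptake (37 vs 27) gives 66%, about 75% (28 vs 20) gives 55%, and about 50% (18 vs 14) gives 42%.

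**The case against.** The strongest defence is that the power claim is correct. The SAP ties 71% to the 10% vs 1% gap, not to the litre figure, and both powers follow from that gap. The bullet is garbled: it opens with the sotagliflozin reduction, names that group, and ends with a word suggesting that a second value was lost. This stands. A reader might infer that the SAP miscalculated its power, and the documents do not support that. The fault is the label on 0.47 L.

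A reader might also take 0.423 L as the sponsor's planned difference. The documents state neither that value nor a 4.7 L baseline, and 0.42 L fits the rounded powers slightly better. The inference is strong, but it needs the sponsor's confirmation.

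A third tempting reading is that real power is near 42%. That rests on one assumed tracer uptake. The documents support only that the design figures are upper values, and the SAP already defines its N as patients with both measurements.

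It can also be said that the outdated design is a version-control matter reaching well beyond power, and that the consequence is modest. Protocol 14.7 makes the main analysis descriptive and the covariance analysis exploratory with a 90% interval, and the SAP calls the study exploratory. A null result should be read mainly from that interval. This limits the weight of the point. It does not justify leaving a superseded power beside a protocol that disclaims any formal calculation.

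**Conclusion.** The point holds as an error of labelling and currency, not of calculation. Under the SAP's stated test and pooled comparison, 0.47 L as a between-group difference gives 79.6% and 68.3%, against a stated 71% and 60%. The stated powers fit a difference of about 0.42 L, so the literal reading overstates the planned effect by about 11% (0.47 / 0.423 = 1.11).

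For the 64-patient design in force, power at about 0.42 L is roughly 66% pooled and 60–61% for 400 mg alone. These values assume an SD of 0.8 L, the inferred baseline of about 4.7 L, and tracer plasma volume at both visits in every patient. They are therefore upper figures with respect to tracer availability. SAP 1.3 also conflicts with protocol 14.1, and protocol 12.3 retains the old total. This affects how the plasma-volume result is interpreted. It does not affect the validity of the estimate.

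**What to change.** In SAP 1.3:

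- Have the sponsor confirm, and then state, that 0.47 L is the assumed reduction within the sotagliflozin group and that the powered difference is 9 percentage points (about 0.42 L). Give the baseline plasma volume used.
- Replace 71% and 60% with the power for the current design (about 66% for pooled 37 vs 27, about 60–61% for 400 mg 27 vs 27), or keep the calculation and mark it as superseded.
- Note that any such figure is an upper value, because it needs both tracer measurements in every patient.

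Then reconcile the two documents: either the SAP calculation is retained as background and labelled so, consistent with protocol 14.1, or 14.1 refers to it. Bring the 81 in protocol 12.3 into line with the 64 in section 8.1.

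The cost is wording in the SAP and two protocol sections. No patients, visits or analyses change. The stated power becomes somewhat less favourable.
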